## **9.6 Safety Extension (Week 12 to Week 24)**

From Week 12 to Week 24, all patients will receive ricolinostat 120 mg daily. Patients will return to the clinic as outlined in the schedule of events and at each visit procedures specified in the schedule of events for that visit will be performed.

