### **9.5.1 Week 1**

The following procedures will be performed at Week 1:

- Administer C-SSRS (Since Last Visit version);
- Obtain vital signs (temperature, respiration rate, pulse, and blood pressure) while patient is sitting after a minimum 5-minute rest. Standing pulse and blood pressure to be obtained following sitting vital signs;
- Perform directed physical exam to assess changes from the prior visit or new concerns;
- Assess skin integrity and wound healing, if applicable;
- Perform 12-lead ECG (after the patient has been resting in the supine position);
- Collect blood samples for the following:
  - Fasting chemistry (fasting of 8-10 hours) and hematology;
- Collect urine samples for the following:
  - Urine pregnancy test (if FOCBP);
  - Urine drug screen (performed at the discretion of the Investigator);
- Record concomitant medications and AEs;
- Collect returned study drug (used and unused bottles) and perform study drug accountability;
- Instruct patient on daily completion of NRS (worst and average pain experienced each day) and rescue medication use, as applicable (at the discretion of the Investigator); and
- Dispense study drug assigned by IRT.

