#### **9.6.2 Week 14**

The following procedures will be performed at Week 14:

- Administer C-SSRS (Since Last Visit version);
- Obtain vital signs (temperature, respiration rate, pulse, and blood pressure) while patient is sitting after a minimum 5-minute rest. Standing pulse and blood pressure to be obtained following sitting vital signs;
- Perform directed physical exam to assess changes from the prior visit or new concerns;
- Assess skin integrity and wound healing, if applicable;
- Collect blood sample for the following:
  - Hematology;
- Collect urine samples for the following:
  - Urine pregnancy test (if FOCBP);
  - Urine drug screen (performed at the discretion of the Investigator);
- Record concomitant medications and AEs;
- Collect returned study drug (used and unused bottles) and perform study drug accountability;

- Instruct patient on daily completion of NRS (worst and average pain experienced each day) and rescue medication use, as applicable (at the discretion of the Investigator); and
- Dispense study drug assigned by IRT.

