#### **9.6.3 Week 18**

The following procedures will be performed at Week 18:

- Administer C-SSRS (Since Last Visit version);
- Obtain vital signs (temperature, respiration rate, pulse, and blood pressure) while patient is sitting after a minimum 5-minute rest. Standing pulse and blood pressure to be obtained following sitting vital signs;
- Perform directed physical exam to assess changes from the prior visit or new concerns;
- Assess skin integrity and wound healing, if applicable;
- Collect blood sample for the following:
  - Hematology;
- Collect urine samples for the following:
  - Urine pregnancy test (if FOCBP);
  - Urine drug screen (performed at the discretion of the Investigator);
- Record concomitant medications and AEs;
- Collect returned study drug (used and unused bottles) and perform study drug accountability;
- Instruct patient on daily completion of NRS (worst and average pain experienced each day) and rescue medication use, as applicable; and
- Dispense study drug assigned by IRT.

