#### **9.6.4 Week 24**

The following procedures will be performed at Week 24:

- Administer C-SSRS (Since Last Visit version);
- Obtain vital signs (temperature, respiration rate, pulse, and blood pressure) while patient is sitting after a minimum 5-minute rest. Standing pulse and blood pressure to be obtained following sitting vital signs;
- Perform directed physical exam to assess changes from the prior visit or new concerns;
- Assess skin integrity and wound healing, if applicable;
- Perform 12-lead ECG (after the patient has been resting in the supine position);

- Collect blood samples for the following:
  - Fasting chemistry (fasting of 8-10 hours), hematology, and HbA1c;
- Collect urine samples for the following:
  - Urinalysis;
  - Urine pregnancy test (if FOCBP);
  - Urine drug screen (performed at the discretion of the Investigator);
- Administer BPI-SF (pain interference section only);
- Administer NTSS-6;
- Perform UENS;
- Administer Norfolk Diabetic QOL-DN;
- Administer PGIC;
- Perform intraepidermal nerve biopsy (eligible patients at selected sites);
- Record concomitant medications and AEs;
- Collect returned study drug (used and unused bottles) and perform study drug accountability;
- Instruct patient on daily completion of NRS (worst and average pain experienced each day) and rescue medication use, as applicable (at the discretion of the Investigator).

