## 9.7 Follow-Up Period (Week 26 and Week 28)

Approximately 2 and 4 weeks after the last dose of study drug, study patients will have follow-up visits during which the assessments specified for those visits will be performed.

### 9.7.1 Week 26

The following procedures will be performed at Week 26:

- Administer C-SSRS (Since Last Visit version);
- Obtain vital signs (temperature, respiration rate, pulse, and blood pressure) while patient is sitting after a minimum 5-minute rest. Standing pulse and blood pressure to be obtained following sitting vital signs;
- Perform directed physical exam to assess changes from the prior visit or new concerns;
- Collect urine samples for the following:
  - Urine pregnancy test (if FOCBP);
  - Urine drug screen (performed at the discretion of the Investigator);

- Administer BPI-SF (pain interference section only);
- Administer NTSS-6;
- Perform UENS;
- Administer Norfolk Diabetic QOL-DN;
- Administer PGIC;
- Record concomitant medications and AEs;
- Instruct patient on daily completion of NRS (worst and average pain experienced each day) and rescue medication use, as applicable (at the discretion of the Investigator).

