### 11.10.2.2 Adverse Events of Special Interest and Monitoring Procedure

The following AEs are designated as events of special interest, and, if observed as treatment-emergent during the study, should be addressed as described below: Anemia, leukopenia, neutropenia, thrombocytopenia, renal impairment, congestive heart failure, suicidality.

Observation	Risk Management
Clinical Laboratory Parameters for Adverse Events of Special Interest	
Cardiac Conduction: QTcF $\geq$ 500 ms or QTcF increase from baseline $\geq$ 60 ms and QTcF $\geq$ 480 ms	
 
For any observed case, the investigator should repeat the ECG assessment twice and compare the average of these 3 measurements of QTcF to the average of the 2 pre-treatment (i.e. screening and baseline) QTcF values
 
If confirmed, patient should be discontinued and appropriate follow-up instituted
 

Anemia: Hemoglobin decrease from baseline $> 2$ g/dL, or a decrease from baseline of at least 1.0 g/dL to a value below 11.5 g/dL (female) or 13 g/dL (male)	
 
For any observed case, repeat laboratory test within one week to confirm: 
 
If the abnormality persists on repeat laboratory test, refer to section 11.10.2.2.1 for additional laboratory monitoring and initiate appropriate medical work-up to assess potential causes.
 
 
 

Leukopenia: White blood cell count $< 2500/\text{mm}^3$ ; or a decrease from baseline $> 1500/\text{mm}^3$	
Neutropenia: Neutrophil count $< 1250/\text{mm}^3$ ; or decrease from baseline $> 500/\text{mm}^3$	
Platelet count $< 100,000/\text{mm}^3$ ; or a decrease from baseline $> 50,000/\text{mm}^3$	
eGFR $< 30 \text{ ml/min}/1.73 \text{ m}^2$	
 
Confirm with repeat test within one week; if confirmed, patient should be discontinued and appropriate follow-up instituted
 

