#### 4.3.4. *Exploratory endpoints*

The exploratory endpoints for this study are:

- Change in intraepidermal nerve fiber density (IENFD) from baseline to Week 24 will be analyzed in a subgroup of approximately 120 patients at selected sites. Note that placebo subjects will have received ricolinostat for 12 weeks, while treated subjects will have received ricolinostat for 24 weeks. There are 4 comparisons of interest for this analysis:
  - Change from baseline in the IENFD in the group of approximately 60 patients that received ricolinostat for 24 weeks.
  - Change from baseline in the IENFD in the group of approximately 60 patients that received ricolinostat for 12 weeks.
  - The difference in the change from baseline in the IENFD in the Intent-to-Treat population at Week 24.
- Other exploratory endpoints may be identified at the time of analysis of the study data.

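### Patients who switch from placebo to ricolinostat at Week 12 have no scheduled on-drug chemistry until Week 24, too late for the eGFR rule to shorten their exposure; adding creatinine to two existing blood draws would fix this cheaply

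*Protocol*

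**What the plan says.** Protocol section 9.6 puts everyone on active drug in the extension: "From Week 12 to Week 24, all patients will receive ricolinostat 120 mg daily". SAP section 4.3.4 spells out what this means for exposure: "Note that placebo subjects will have received ricolinostat for 12 weeks, while treated subjects will have received ricolinostat for 24 weeks".

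Chemistry is scheduled at Screening, Day 1 and Weeks 1, 4, 12, 24 and 28. At Week 1 the blood tests are "Fasting chemistry (fasting of 8-10 hours) and hematology", and Week 4 has the same entry. Sections 9.6.2 ("The following procedures will be performed at Week 14") and 9.6.3 ("The following procedures will be performed at Week 18") list hematology as the only blood test, and the only urine tests there are for pregnancy and drugs. At Week 24 the list is again "Fasting chemistry (fasting of 8-10 hours), hematology, and HbA1c". SAP Exhibit 3 agrees with these visit lists. Section 9.7 places the two follow-up visits "Approximately 2 and 4 weeks after the last dose of study drug", so dosing stops at about Week 24.

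Protocol section 11.10.2.2 names renal impairment as an event of special interest. For an eGFR below 30 mL/min/1.73 m² the instruction is: "Confirm with repeat test within one week; if confirmed, patient should be discontinued and appropriate follow-up instituted". Appendix I lists creatinine and calculated creatinine clearance under chemistry. eGFR is not listed by name, but it would come from the same sample.

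**The concern.** The chemistry schedule follows time since randomization, not time since first exposure. For patients randomized to ricolinostat the two coincide, and they are tested early and repeatedly on drug. For patients randomized to placebo, the Week 12 sample is taken at the visit where extension drug is dispensed, so it is their last pre-exposure value. Their first 12 weeks on ricolinostat then pass without a scheduled creatinine, although blood is drawn twice.

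What is at stake is the usefulness of a rule that the protocol itself sets. If eGFR falls without symptoms in a switcher, the first routine value that could show it arrives as dosing is ending. The event would still be recorded at Week 24 and checked at Week 28. What is lost is the chance to stop the drug sooner. Section 11.10.1.1 relies on central-laboratory alerts to pick up safety problems early, and no chemistry alert can arise from a sample that is not tested for chemistry.

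**Working it through.** The plan states no figure for this interval, so the check is a visit-schedule calculation.

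**Inputs.** Visit windows from Protocol Table 1: Week 1 = Day 5–9, Week 4 = Day 26–30, Week 12 = Day 82–86, Week 14 = Day 96–100, Week 18 = Day 124–128, Week 24 = Day 166–170. Target days from SAP Exhibit 4: 84, 98, 126 and 168 for Weeks 12, 14, 18 and 24. First ricolinostat dose: Day 1 for patients randomized to ricolinostat; for switchers it is taken as the day of the Week 12 visit. If it is the next morning, each switcher interval is one day shorter.

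**Formula.** Shortest interval = earliest day of the later visit − latest day of the earlier visit. Longest interval = latest day of the later visit − earliest day of the earlier visit.

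**Patients randomized to ricolinostat, days from first dose to chemistry**
- Week 1: 5 − 1 = 4 to 9 − 1 = 8
- Week 4: 26 − 1 = 25 to 30 − 1 = 29
- Week 12: 82 − 1 = 81 to 86 − 1 = 85

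**Switchers who stay on drug, days from the Week 12 visit**
- Week 24, the first chemistry as planned: 166 − 86 = 80 to 170 − 82 = 88; nominal 168 − 84 = 84
- Week 14, hematology only as planned: 96 − 86 = 10 to 100 − 82 = 18; nominal 98 − 84 = 14
- Week 18, hematology only as planned: 124 − 86 = 38 to 128 − 82 = 46; nominal 126 − 84 = 42

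Scheduled chemistry tests in switchers after the switch and before Week 24: 0. Scheduled blood draws in the same interval: 2.

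**With chemistry added at Weeks 14 and 18.** Nominal steps are 98 − 84 = 14, 126 − 98 = 28 and 168 − 126 = 42 days. The first on-drug value moves from 80–88 days to 10–18 days, and the longest nominal gap falls from 84 to 42 days.

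**Whether the rule could then act.** Allow the full 7 days for the repeat test. A fall first seen at Week 14 is confirmed by nominal day 14 + 7 = 21 of the extension, leaving 84 − 21 = 63 dosing days. One first seen at Week 18 is confirmed by day 42 + 7 = 49, leaving 35. One first seen at Week 24 leaves none. These figures describe what the schedule allows; they are not expected savings per patient.

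**Number of assays.** Taking all 274 planned patients into the extension, 274 × 2 = 548. With an assumed dropout of 10% to 30%, 548 × 0.9 = 493 and 548 × 0.7 = 384. Any benefit would shrink with dropout in the same way.

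**The case against.** The strongest reply is that this is a reasonable judgment about monitoring intensity and that nothing in the plan breaks.

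- Section 11.9 says that existing data do not point to added renal risk, and attributes earlier renal changes to myeloma and concurrent chemotherapy. The same passage, however, says that these risks need monitoring.
- Chemistry is sparse for everyone. There is none between Weeks 4 and 12 (nominal 84 − 28 = 56 days) or between Weeks 12 and 24. True, but patients randomized to ricolinostat enter those gaps with two and three on-drug values. Switchers enter theirs with none.
- Switchers have five scheduled pre-switch chemistries (Screening, Day 1, Weeks 1, 4 and 12). An eGFR below 45 is excluded at entry, so someone entering at the limit must fall by more than 45 − 30 = 15 to meet the rule. This lowers the risk but says nothing about response to the drug.
- The unblinded DMC sees on-drug chemistry from the randomized arm, and section 11.4 lets sample times be refined on emerging data. A drug-wide signal could therefore be acted on. But refinement is discretionary, and the DMC cannot review an individual value that was not collected.
- Early-termination assessments (section 9.8) include chemistry, but only for those who stop. Symptoms or abnormal findings can prompt unscheduled tests, so the gap concerns patients without symptoms. The COVID-19 limit on time without laboratory tests (section 13.2) does not name chemistry, and hematology would satisfy it.

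Together these points justify a low priority. None of them gives a switcher who remains on drug a routine creatinine in time to stop early.

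**Conclusion.** The point stands as a low-cost improvement of modest importance. The scheduled interval from the switch to a first on-drug chemistry is 80 to 88 days, against 4 to 8 days in the randomized ricolinostat arm. It rests only on the visit windows and on first extension dosing at about the Week 12 visit.

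Two stronger readings are not supported. A reader might infer that the eGFR rule has no routine trigger in switchers. It has one at Week 24; the trigger is late, not absent. A reader might also infer that a certain number of patients will be harmed or would be caught earlier. The documents give no rate for eGFR below 30 and nothing on when such falls begin, and some would have causes unrelated to the drug. Any count of patients caught or average of dosing days saved would be an assumption, so none is offered here. No harm is demonstrated, and no efficacy analysis or planned safety summary is affected.

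**What to change.** Amend Protocol Table 1, sections 9.6.2 and 9.6.3, and SAP Exhibit 3 to add creatinine with eGFR to the existing Week 14 and Week 18 blood draws. The full chemistry panel is optional. Because Table 1 specifies fasting for chemistry, the amendment should say whether a creatinine-only sample at these visits needs it.

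Apply the change to all extension patients. Original assignment stays blinded until the first database lock (Protocol section 7.4.3, SAP section 5.2), and testing only switchers before then would reveal it.

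The cost is up to 548 extra central-laboratory assays, possibly one more tube per draw, fasting at two visits if the full panel is run, some repeat tests including false alarms, and an amendment with IRB review at about 50 sites. About half the assays go to patients who already have on-drug values; that is the price of keeping the blind. No new visit or venipuncture is needed, and under section 13.2 a home health nurse can already draw safety laboratory samples at remote visits. The change could be combined with any other amendment.

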### **9.6.1 Week 12**

The following procedures will be performed at Week 12:

- Administer C-SSRS (Since Last Visit version);
- Obtain vital signs (temperature, respiration rate, pulse, and blood pressure) while patient is sitting after a minimum 5-minute rest. Standing pulse and blood pressure to be obtained following sitting vital signs;
- Perform directed physical exam to assess changes from the prior visit or new concerns;
- Assess skin integrity and wound healing, if applicable;
- Perform 12-lead ECG (after the patient has been resting in the supine position);
- Collect blood samples for the following:

- Fasting chemistry (fasting of 8-10 hours), hematology, and HbA1c;
- Collect urine samples for the following:
  - Urinalysis;
  - Urine pregnancy test (if FOCBP);
  - Urine drug screen (performed at the discretion of the Investigator);
- Administer BPI-SF (pain interference section only);
- Administer NTSS-6;
- Perform UENS;
- Administer Norfolk Diabetic QOL-DN;
- Administer PGIC;
- Record concomitant medications and AEs;
- Collect returned study drug (used and unused bottles) and perform study drug accountability;
- Instruct patient on daily completion of NRS (worst and average pain experienced each day) and rescue medication use, as applicable (at the discretion of the Investigator); and
- Dispense study drug assigned by IRT.

#### **9.6.2 Week 14**

The following procedures will be performed at Week 14:

- Administer C-SSRS (Since Last Visit version);
- Obtain vital signs (temperature, respiration rate, pulse, and blood pressure) while patient is sitting after a minimum 5-minute rest. Standing pulse and blood pressure to be obtained following sitting vital signs;
- Perform directed physical exam to assess changes from the prior visit or new concerns;
- Assess skin integrity and wound healing, if applicable;
- Collect blood sample for the following:
  - Hematology;
- Collect urine samples for the following:
  - Urine pregnancy test (if FOCBP);
  - Urine drug screen (performed at the discretion of the Investigator);
- Record concomitant medications and AEs;
- Collect returned study drug (used and unused bottles) and perform study drug accountability;

- Instruct patient on daily completion of NRS (worst and average pain experienced each day) and rescue medication use, as applicable (at the discretion of the Investigator); and
- Dispense study drug assigned by IRT.

#### **9.6.3 Week 18**

The following procedures will be performed at Week 18:

- Administer C-SSRS (Since Last Visit version);
- Obtain vital signs (temperature, respiration rate, pulse, and blood pressure) while patient is sitting after a minimum 5-minute rest. Standing pulse and blood pressure to be obtained following sitting vital signs;
- Perform directed physical exam to assess changes from the prior visit or new concerns;
- Assess skin integrity and wound healing, if applicable;
- Collect blood sample for the following:
  - Hematology;
- Collect urine samples for the following:
  - Urine pregnancy test (if FOCBP);
  - Urine drug screen (performed at the discretion of the Investigator);
- Record concomitant medications and AEs;
- Collect returned study drug (used and unused bottles) and perform study drug accountability;
- Instruct patient on daily completion of NRS (worst and average pain experienced each day) and rescue medication use, as applicable; and
- Dispense study drug assigned by IRT.

#### **9.6.4 Week 24**

The following procedures will be performed at Week 24:

- Administer C-SSRS (Since Last Visit version);
- Obtain vital signs (temperature, respiration rate, pulse, and blood pressure) while patient is sitting after a minimum 5-minute rest. Standing pulse and blood pressure to be obtained following sitting vital signs;
- Perform directed physical exam to assess changes from the prior visit or new concerns;
- Assess skin integrity and wound healing, if applicable;
- Perform 12-lead ECG (after the patient has been resting in the supine position);

- Collect blood samples for the following:
  - Fasting chemistry (fasting of 8-10 hours), hematology, and HbA1c;
- Collect urine samples for the following:
  - Urinalysis;
  - Urine pregnancy test (if FOCBP);
  - Urine drug screen (performed at the discretion of the Investigator);
- Administer BPI-SF (pain interference section only);
- Administer NTSS-6;
- Perform UENS;
- Administer Norfolk Diabetic QOL-DN;
- Administer PGIC;
- Perform intraepidermal nerve biopsy (eligible patients at selected sites);
- Record concomitant medications and AEs;
- Collect returned study drug (used and unused bottles) and perform study drug accountability;
- Instruct patient on daily completion of NRS (worst and average pain experienced each day) and rescue medication use, as applicable (at the discretion of the Investigator).

## 9.7 Follow-Up Period (Week 26 and Week 28)

Approximately 2 and 4 weeks after the last dose of study drug, study patients will have follow-up visits during which the assessments specified for those visits will be performed.

### 9.7.1 Week 26

The following procedures will be performed at Week 26:

- Administer C-SSRS (Since Last Visit version);
- Obtain vital signs (temperature, respiration rate, pulse, and blood pressure) while patient is sitting after a minimum 5-minute rest. Standing pulse and blood pressure to be obtained following sitting vital signs;
- Perform directed physical exam to assess changes from the prior visit or new concerns;
- Collect urine samples for the following:
  - Urine pregnancy test (if FOCBP);
  - Urine drug screen (performed at the discretion of the Investigator);

- Administer BPI-SF (pain interference section only);
- Administer NTSS-6;
- Perform UENS;
- Administer Norfolk Diabetic QOL-DN;
- Administer PGIC;
- Record concomitant medications and AEs;
- Instruct patient on daily completion of NRS (worst and average pain experienced each day) and rescue medication use, as applicable (at the discretion of the Investigator).

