During the 12-week randomized, double-blind, placebo-controlled Treatment period, patients will return for assessments as per the schedule of assessments shown in [Table 1](#). An electronic daily diary will be completed by patients to record study and rescue medication (acetaminophen) use, as well as NRS pain assessments. Rescue medication (as needed) and one permitted medication that has been used at a stable dose for at least 3 months prior to starting the Pain Observation period may be used during the study. Other pain medications are prohibited during the Treatment period. Diary data will be reviewed with the patient at each study visit to determine if further instruction is required and to document any discrepancies with study drug or rescue medication dosing.

At the conclusion of the approximately 12-week double-blind, placebo-controlled Treatment period, patients will enter an approximately 12-week open label Safety Extension period during which all patients will receive ricolinostat 120 mg daily and complete evaluations and clinic visits as per the schedule of events. At the conclusion of the Safety Extension, there will be an approximately 4-week washout and Safety Follow-up period, which will incorporate 2 visits at approximately 2 and 4 weeks following the final Safety Extension visit, with assessments performed as outlined in the schedule of assessments ([Table 1](#)).

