#### **9.7.2 Week 28**

The following procedures will be performed at Week 28:

- Administer C-SSRS (Since Last Visit version);
- Obtain vital signs (temperature, respiration rate, pulse, and blood pressure) while patient is sitting after a minimum 5-minute rest. Standing pulse and blood pressure to be obtained following sitting vital signs;
- Perform directed physical exam to assess changes from the prior visit or new concerns;
- Assess skin integrity and wound healing, if applicable;
- Collect blood samples for the following:
  - Fasting chemistry (fasting of 8-10 hours), hematology, and HbA1c;
- Collect urine samples for the following:
  - Urine pregnancy test (if FOCBP);
  - Urine drug screen (performed at the discretion of the Investigator);
- Record concomitant medications and AEs.

At the conclusion of these evaluations, the patient will have completed the study.

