#### 6.1.4. *Visit windows*

Analysis visits and their windows are defined using derived study day (Section 6.1.3) instead of relying on visit labels in the clinical database because clinical visits may occur outside protocol-specified windows. Study day and days after last dose are calculated using the actual date of each scheduled and unscheduled assessment and compared to the target for each analysis visit as specified in Exhibit 4.

If a parameter is assessed or measured more than once within a visit window, the one that is closest to the protocol-scheduled time point (i.e., target) is used for the purposes of data analysis and summary. If two assessments are equidistant from a target, the earlier assessment is used. If the visit used for analysis includes two assessments on the same day, the average of the two measurements is used.

Records from visits not closest to the target study day, and therefore not used in analyses, are presented in by-subject data listings.

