**Exhibit 4. Example of study days and analysis timepoints**

Analysis visit	Label	Study day a	Analysis window
0	Day 1 b	1	1
1	Week 1	5	2 ≤ study day ≤ 9
2	Week 2	14	10 ≤ study day ≤ 18
4	Week 4	28	24 ≤ study day ≤ 32
8	Week 8 c	56	52 ≤ study day ≤ 60
12	Week 12 d	84	14 ≤ days after last dose ≤ 32
14	Week 14	98	94 ≤ study day ≤ 102
18	Week 18	126	122 ≤ study day ≤ 130
24	Week 24 e	168	164 ≤ study day ≤ 172
26	Week 26 f	182	14 ≤ days after last dose ≤ 32
28	Week 28	196	192 ≤ study day ≤ 200

a) Study Day is relative to the date of randomization (Section 6.1.3).

b) Day 1 is the last measurement prior to the first study drug administration.

c) Week 8 is the end of the double-blind, placebo-controlled treatment period.

d) Week 12 is the start of the open-label safety extension period.

e) Week 24 is the end of the open-label safety extension period.

f) Week 26 is the start of the follow-up period.

*6.1.5. Procedures for handling missing data*

*6.1.5.1. Missing data on the primary efficacy endpoint*

The primary efficacy endpoint (e.g., NRS) is captured in a daily log. Missing daily NRS entries will be handled by performing a simple weekly average of the daily scores so long as four or more entries occur during the week. If three or fewer entries occur during the week, then the scores' weekly average will be set to missing for that week. Missing values will be multiple imputed using missing at random multiple imputation for intermittent missing values and reference-based imputation for all other missing data. These data will be part of the blinded data review with the option to change the approach to the summary score during the blinded data review process.

*6.1.5.2. Missing UENS*

The key secondary endpoint will be analyzed using missing at random imputation for intermittent missing data and reference-based imputation for all other missing data.

*6.1.5.3. Missing data for secondary endpoint*

Missing values for secondary endpoints will not be imputed. All results will be analyzed under the complete case scenario.

*6.1.5.4. Missing or partial stop- or start-dates for adverse events*

Missing or partial stop- or start-dates for adverse events will be imputed using the most conservative (e.g., worst case scenario) assumption. In all cases of missing or partial information, the site will be instructed to attempt to obtain the missing details. The rules for imputation follow:

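### SAP Exhibit 4's Week 26 window (14 to 32 days after last dose) also admits on-schedule Week 28 visits and leaves some on-schedule Week 26 visits in no window

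*Protocol*

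**What the plan says.** Protocol section 9.7 states: "Approximately 2 and 4 weeks after the last dose of study drug, study patients will have follow-up visits". Section 7.1 anchors the same visits slightly differently, as "2 visits at approximately 2 and 4 weeks following the final Safety Extension visit". Table 1 of the protocol places them at Days 180 to 184 (Week 26) and Days 194 to 198 (Week 28), after a Week 24 visit on Days 166 to 170.

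The two visits collect different things. Section 9.7.1 (Week 26) lists BPI-SF, NTSS-6, UENS, Norfolk QOL-DN and PGIC but no blood sample. Section 9.7.2 (Week 28) lists "Fasting chemistry (fasting of 8-10 hours), hematology, and HbA1c" but none of those five scales. Vital signs are taken at both.

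SAP section 6.1.4 assigns records to analysis visits by date rather than by visit label: "Study day and days after last dose are calculated using the actual date of each scheduled and unscheduled assessment", and these are compared with the targets in Exhibit 4. The relevant rows of Exhibit 4 are:

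- Week 24: target Day 168, "164 ≤ study day ≤ 172"
- Week 26: target Day 182, "14 ≤ days after last dose ≤ 32"
- Week 28: target Day 196, "192 ≤ study day ≤ 200"

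For several records in one window, the rule is: "If a parameter is assessed or measured more than once within a visit window, the one that is closest to the protocol-scheduled time point" is used. Nothing is said about one record that meets two windows.

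**The concern.** The Week 26 row counts from last dose, while the rows on either side count from randomization. Its 14-to-32-day span is wide enough to hold both follow-up visits, and it starts exactly at the planned Week 26 day instead of being centred on it. Two problems follow.

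- **Overlap.** A Week 28 record can meet the Week 26 definition as well. No blood is scheduled at Week 26, so the Week 28 sample would be the only scheduled laboratory record eligible for that row. A four-week off-drug value could then be read as a two-week one.
- **Gap.** A Week 26 visit that is on schedule but less than 14 days after last dose belongs to no analysis visit. For measures taken at both visits, such as vital signs, the Week 28 record would then take the Week 26 slot. For UENS, NTSS-6, BPI-SF, QOL-DN and PGIC, the only scheduled values after treatment ends would have no slot at all.

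Blood counts are among the trial's events of special interest, so a by-visit description of what happens after stopping drug should carry the right time label.

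**Working it through.** **Target.** 26 × 7 = 182, and 168 + 14 = 182. The Exhibit 4 target for Week 26 is therefore consistent with the protocol. The window around it is not.

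**Inputs.** The scheduled days come from protocol Table 1: Week 24 = 168 + a, Week 26 = 182 + b, Week 28 = 196 + c, with a, b and c each from −2 to +2. The windows come from Exhibit 4. The documents do not say whether the last dose falls on the Week 24 visit day or the day before, so both are shown, with lag g = 0 or 1.

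**Formulas.**

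- Days from last dose to Week 26 = (182 + b) − (168 + a − g) = 14 + b − a + g
- Days from last dose to Week 28 = (196 + c) − (168 + a − g) = 28 + c − a + g

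**Results by day of last dose.**

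| Last dose (study day) | Week 26 window in study days | Scheduled Week 26 days (180–184) in no window | Scheduled Week 28 days (194–198) in both windows |
|---|---|---|---|
| 165 | 179–197 | 0 | 4 |
| 166 | 180–198 | 0 | 5 |
| 167 | 181–199 | 1 (180) | 5 |
| 168 | 182–200 | 2 (180, 181) | 5 |
| 169 | 183–201 | 3 (180–182) | 5 |
| 170 | 184–202 | 4 (180–183) | 5 |

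The missed Week 26 days fall in no other window either, because Week 24 ends at Day 172 and Week 28 starts at Day 192. With last dose on Day 168, the Week 26 window (182–200) contains the entire Week 28 window (192–200).

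**Totals over the 25 allowed day pairs.**

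- Last dose on the Week 24 visit day (rows 166–170): Week 26 in no window, 0 + 1 + 2 + 3 + 4 = 10 of 25 (40%). Week 28 in both windows, 25 of 25; the interval runs from 24 to 32 days.
- Last dose the day before (rows 165–169): Week 26 in no window, 0 + 0 + 1 + 2 + 3 = 6 of 25 (24%). Week 28 in both windows, 4 + 5 + 5 + 5 + 5 = 24 of 25 (96%); the interval runs from 25 to 33 days.

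These shares treat visit days as independent and equally likely, which is an assumption. If Week 26 is booked exactly 14 days after last dose, the visit is on the boundary and inside, so the missed share is 0%. If it is booked from last dose with an even ±2-day spread, days 12 and 13 are missed out of 12 to 16: 2 of 5, or 40%.

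**Check of a study-day window.** 182 ± 4 gives 178 to 186. It contains every scheduled Week 26 day (180–184) and no scheduled Week 28 day (194–198).

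**The case against.** The strongest reply is that little depends on this row.

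- SAP section 1 says that the SAP governs where it differs from the protocol. SAP 11.2 summarises laboratory values at screening, discharge and end of study, and SAP 11.4 summarises vital signs at screening, pre-dose and hours after dosing. Neither names Week 26.
- Every planned analysis of UENS, NTSS-6, BPI-SF, QOL-DN and PGIC is at Week 4, Week 12 or both.
- Section 6.1.4 keeps unused records in by-subject listings.
- Hematological events of special interest are confirmed patient by patient from dated samples (protocol 11.10.2.2.1), without using Exhibit 4.
- Exhibit 4 is headed as an example.
- The 24% to 40% depends on how visits are booked and can be 0%.

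Most of this stands, and it limits the point to descriptive follow-up summaries. It does not make the row correct. Section 6.1.4 refers to Exhibit 4 for the windows, and the SAP gives no others. Protocol 10.3.7 calls for hematology and chemistry by visit, and the discharge time point in SAP 11.2 corresponds to no visit in this trial. Anyone producing by-visit tables would have to use Exhibit 4.

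A reader might infer that Week 28 blood results will be reported as Week 26 results. The documents do not go that far. They let the sample qualify for both rows and are silent on whether one record may fill two, and a Week 26 laboratory row need not be produced at all.

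One could also defend the dose-date anchor because section 9.7 counts from last dose. But section 7.1 counts from the final Safety Extension visit, and Table 1 gives study days, so a study-day window is equally faithful to the protocol.

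**Conclusion.** The point holds as a windowing error in SAP Exhibit 4; the protocol text on the two follow-up visits is not at fault. For patients who complete treatment, 24 or 25 of 25 allowed day pairs put an on-schedule Week 28 visit inside the Week 26 window, depending on whether the last dose is the day before or the day of the Week 24 visit. An on-schedule Week 26 visit fewer than 14 days after last dose has no analysis visit. That share ranges from 0% (booked exactly at 14 days) to 24% to 40% of allowed day pairs (independent, evenly spread visit days). The actual share depends on visit and last-dose dates, which the documents do not give; the boundary fault itself does not depend on it.

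The consequence is limited to possible mislabelling or loss of records in descriptive by-visit follow-up summaries. Primary, key secondary and secondary analyses do not use Week 26. The correction is worth making because it is almost free.

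**What to change.** In Exhibit 4, replace the Week 26 window with 178 ≤ study day ≤ 186, which follows the ±4-day pattern already used for Weeks 14, 18, 24 and 28. Add one sentence to SAP section 6.1.4 stating that each record is assigned to one analysis visit only.

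Correct the Week 12 row at the same time. It carries the same 14-to-32-day text, although the Week 12 visit (Days 82 to 86) takes place while patients are still on study drug and is where the key secondary UENS is measured. The same ±4-day pattern around its stated target would be 84 ± 4, or Days 80 to 88.

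The cost is two table rows and one sentence in the SAP, with no change to data collection. A separate summary of post-treatment records from patients who stop early is optional and would be a new output.
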